### 5.3. Immunogenicity Analysis

The analysis of immunogenicity will use the PPI set. For both the Immuno subset and the Revaccination Subcohorts, the immunogenicity analysis will follow the analysis outlined in Section 4.3. Except for Revaccination Subcohort B, Post-F ELISA results will no longer be assessed from Day 365 onwards for the Immuno Subset and Revaccination Subcohorts A, C and D.

In addition, for each Revaccination Subcohort separately, geometric mean ratios and corresponding 95% CIs between Day 15 post first vaccination and Day 15 post second vaccination within the group receiving active study vaccine on Day 1 (group 1A, 1B, 1C and 1D respectively) will be calculated for the different assays.

Moreover, the GMT ratios with corresponding 95% CIs of Day 15 post second vaccination for the group receiving active study vaccine twice versus the group receiving placebo first and active study vaccine 1, 2, 3 or 4 years later will also be calculated for the different assays. Therefore, an analysis of variance (ANOVA) model will be fitted with the respective titers as dependent variable and group as independent variable. The point estimate and CIs obtained as such will be back transformed (by exponentiation) to a GMT ratio and the corresponding CI. As a sensitivity analysis, different variances between the groups will be allowed, therefore the CIs will be calculated via Welch's ANOVA.

A similar analysis might be performed at other timepoints as well.

For Revaccination Subcohorts 2A and 2B that get a third vaccination with Ad26.RSV.preF/RSV preF protein mixture or with the individual vaccine components, no formal hypothesis is tested; descriptive statistics over time after the third vaccination will be calculated.

Graphical representations of immunogenicity parameters will be made as applicable.

The impact of baseline factors on the humoral responses will be explored graphically or via descriptive statistics.

Note that tables including descriptive statistics of actual values and fold changes (if applicable) over time might also once be calculated restricted to participants who have data at the last scheduled timepoint included in the respective analyses of the immunosubset and Revaccination Subcohorts. This might also be graphically shown.

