### 1.2. Study Design

This is a multi-center, randomized, double-blind, placebo-controlled Phase 2b proof-of-concept study in male and female participants aged  $\geq 65$  years who are in stable health. A target of up to 5,800 participants (Cohort 1) will be enrolled and randomized in parallel in a 1:1 ratio to 1 of 2 groups to receive Ad26.RSV.preF/RSV preF protein mixture or placebo intramuscularly ([Table 1](#)).

At Day 365, a subcohort of Cohort 1 participants will be identified and will be revaccinated, to assess safety and immunogenicity of a second vaccination. This Revaccination Subcohort (N=240) will consist of at least 120 participants who received active study vaccine on Day 1 and 120 participants who received placebo on Day 1, and who have given informed consent for the additional study procedures. Additional Revaccination Subcohorts were implemented. Participants in these additional Revaccination Subcohorts will receive a revaccination with active study vaccine at 2, 3, or 4 years after the first vaccination to assess the safety and immunogenicity of revaccination with Ad26.RSV.preF/RSV preF protein mixture or with the individual vaccine components as indicated in the table below ([Table 1](#)).

During all 3 RSV seasons, as well as between the second and third RSV season, participants in cohort 1 will be followed-up twice per week to monitor for symptoms that could indicate an ARI. For participants in the Revaccination Subcohorts, follow-up of ARIs will stop at the end of the second RSV season for Subcohort A, at the Day 730 (Month 24) visit for Subcohort B, and at the latest at the end of the third RSV season for Subcohorts C and D. Please refer to Section 3.1 in the CTP for further details.

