## **2. GENERAL ANALYSIS DEFINITIONS**

### **2.1. Study Phases**

A baseline (or reference) value for safety and immunogenicity will be defined as the value of the last available assessment prior to the first vaccination on Day 1. If there was no immunogenicity assessment done pre-vaccination, the assessment post-vaccination on Day 1 can be used as the baseline value for the immunogenicity analysis, if available.

A baseline (or reference) value for the efficacy analysis of the first RSV season will be defined as the worst value of the available assessment at Day 1 visit, if Day 1 visit is not available the Day 1 unscheduled visit closest to the day of vaccination will be used. In case two or more assessments are available at the same visit or at the same day of the selected baseline visit (for example assessments both at the eDiary and eDevice) the worst will be used (per question).

A new baseline (or reference) value for the efficacy analysis of the second and third RSV season will be defined as the worst value of the available assessment at Day 365/Day 730 visit, if Day 365/Day 730 visit is not available the Day 365/Day 730 unscheduled visit closest to the relative day 365/day 730 will be used. In case no Day 365/Day 730 visit (schedule or unscheduled) is available then the baseline of the first/second (or first) RSV season will be used. In case two or more assessments are available at the same visit or at the same day of the selected baseline visit (for example assessments both at the eDiary and eDevice) the worst value will be used (per question).

The safety analysis will present all results by period, unless specified otherwise. Immunogenicity results will be presented per analysis time point (see Section 2.1.2) as appropriate. Listings will be shown per phase, period and time point. Efficacy results will be presented across the entire season or per timepoint, where appropriate.

Study day or relative day is defined as follows:

Study Day = visit date - date of Day 1 + 1; if visit date > date of Day 1 (date of first vaccination).

Study Day = visit date - date of Day 1; if visit date < date of Day 1 (date of first vaccination).

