### 2.1.2. Immunogenicity Visit Windows

For immunogenicity summaries and tabulations per time point, assessments will be allocated to an analysis visit based on the planned visit as captured in the CRF. Visits that are out of the protocol-defined visit windows (see table below) will not be included in the immunogenicity summaries and tabulations per timepoint. However, they may be included in sensitivity analyses.

Analysis timepoint	Subset	Reference day	Target day (counted from the reference day)	Window
Baseline	Immuno Subset / All Revaccination Subcohorts	Day of vaccination 1	1	(-inf, 1]
Day 15	Immuno Subset / All Revaccination Subcohorts	Day of vaccination 1	15	[15, 18]
Day 85	Immuno Subset	Day of vaccination 1	85	[78, 92]
Day 169	Immuno Subset	Day of vaccination 1	169	[155, 183]
Day 365	Immuno Subset / Revaccination Subcohort 1B, 2B, 1C, 2C, 1D and 2D	Day of vaccination 1	365	[304, 426]
Day 365	Revaccination Subcohorts 1A, 2A	Day of vaccination 2	1	[1]
Day 379	Revaccination Subcohorts 1A, 2A	Day of vaccination 2	15	[15, 18]
Day 393	Revaccination Subcohorts 1A, 2A	Day of vaccination 2	29	[29, 32]
Day 449	Revaccination Subcohorts 1A, 2A	Day of vaccination 2	85	[78, 92]
Day 533	Immuno Subset	Day of vaccination 1	533	[519, 547]
Day 533	Revaccination Subcohorts 1A, 2A	Day of vaccination 2	169	[155, 183]
Day 730	Immuno Subset	Day of vaccination 1	730	[669, 791]
Day 730	Revaccination Subcohort 1A	Day of vaccination 2	365	[334,396]
Day 730	Revaccination Subcohort 1B, 2B	Day of vaccination 2	1	[1]
Day 730	Revaccination Subcohort 2A	Day of vaccination 3	1	[1]
Day 737	Revaccination Subcohort 1B, 2B	Day of vaccination 2	8	[6, 10]
Day 737	Revaccination Subcohort 2A	Day of vaccination 3	8	[6, 10]
Day 744	Revaccination Subcohort 1B, 2B	Day of vaccination 2	15	[15, 18]
Day 744	Revaccination Subcohort 2A	Day of vaccination 3	15	[15, 18]
Day 758	Revaccination	Day of vaccination 2	29	[29, 32]

Analysis timepoint	Subset	Reference day	Target day (counted from the reference day)	Window
	Subcohort 1B, 2B			
Day 758	Revaccination Subcohort 2A	Day of vaccination 3	29	[29, 32]
Day 814	Revaccination Subcohort 1B, 2B	Day of vaccination 2	85	[78, 92]
Day 814	Revaccination Subcohort 2A	Day of vaccination 3	85	[78, 92]
Day 898	Revaccination Subcohort 1B, 2B	Day of vaccination 2	169	[155, 183]
Day 898	Revaccination Subcohort 2A	Day of vaccination 3	169	[155, 183]

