#### 4.3.4.1. Immunogenicity Against the Insert:

##### 4.3.4.1.1. Humoral Assays

For VNA and ELISA assays following results will be calculated: N, geometric mean§ and corresponding 95% CI of the actual values and fold increases from baseline will be tabulated and graphically presented. *§calculate the mean and corresponding 95%CI of the log2 transformed values, back-transform this mean [i.e. 2mean] and CI [i.e. 2CI].*

Actual values and fold changes from baseline are tabulated and shown as dot plots with dots for subject values, and the corresponding geometric mean and 95% CI per time point for each assay. In addition, GMT plots over time, combining the regimens in one graph (without individual subject dots) will also be created.

Ratios of actual values and of fold changes from baseline between humoral assays may also be presented.

Subject profiles of the actual values over time will be graphically presented.

Reverse distribution curves of the actual values will be provided for selected time points.

In the graphs, original values will be displayed on the log2 scale.

A scatterplot with the VNA versus ELISA will be provided for the most important time points. In these scatterplots the actual values will be shown, even if they are below the LLOQ, but the LLOQ cut-off will be visualized in the graph per assay if some values are below LLOQ.

Other exploratory parameters maybe analyzed at the discretion of the sponsor.

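### The revaccination GMT-ratio model adjusts for nothing, although a pre-vaccination titer and two stratification factors are available in every Revaccination Subcohort; the interval is valid but less precise than it could be

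*SAP*

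**What the plan says.** SAP Section 5.3 compares, in each Revaccination Subcohort, participants who received active vaccine twice with those who received placebo first and active vaccine one to four years later. The GMT ratio is taken at Day 15 after the second vaccination. For this, "an analysis of variance (ANOVA) model will be fitted with the respective titers as dependent variable and group as independent variable". One alternative is planned: "As a sensitivity analysis, different variances between the groups will be allowed, therefore the CIs will be calculated via Welch's ANOVA". It relaxes the variance assumption and adds no covariate. Otherwise, "The impact of baseline factors on the humoral responses will be explored graphically or via descriptive statistics".

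The covariate is already collected. In the visit-window table of Section 2.1.2, the Baseline row applies to "Immuno Subset / All Revaccination Subcohorts", with a window that closes on the day of the first vaccination. Section 2.1 defines the immunogenicity baseline as "the value of the last available assessment prior to the first vaccination on Day 1", with a post-vaccination Day 1 sample as fallback.

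The primary efficacy model in Section 4.4.2.2 includes age and increased-risk status as stratified. Section 5.3 uses neither in the GMT-ratio model.

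**The concern.** If titers before the first vaccination predict titers after revaccination, a group-only model leaves explainable variation in the residual and gives a wider interval than the data allow. It also passes any baseline difference between the groups into the ratio.

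Baseline difference deserves more thought here than in an intact randomised comparison. The subcohorts consist of participants who gave separate consent (Table 1, footnote c) and were revaccinated one to four years after Day 1. The PPI population (Section 2.3.2) drops samples taken after natural RSV infection, after relevant major deviations or outside the visit windows. If the vaccine prevents infection, the first of these exclusions could remove more placebo-first participants. The groups compared are then not purely as randomised.

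At stake is the precision of the only model-based between-group estimate in Section 5.3, which is produced for four subcohorts and several assays.

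**Working it through.** The SAP states no SD, correlation, precision target or power for this ratio, so there is no figure of its own to reproduce. The check compares the expected 95% CI half-width with and without the baseline titer.

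**Inputs from the SAP**
- Group size n: for Subcohort A, "at least 120 participants who received active study vaccine on Day 1 and 120 participants who received placebo on Day 1" (Section 1.2). Table 1 gives 120 per group for C and D as well, and 135 for B.
- Scale: log2. Section 4.3.4.1.1 says to "calculate the mean and corresponding 95%CI of the log 2 transformed values" and back-transform.

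**Assumptions, not in the SAP**
- rho, the within-group correlation of baseline log titer with Day 15 post-second-vaccination log titer: 0 to 0.7.
- SD of the log2 titer: 1.5, used only to express results as fold factors.

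**Formulas**
- ANOVA half-width = t(0.975, 2n-2) × SD × sqrt(2/n)
- ANCOVA half-width = t(0.975, 2n-3) × SD × sqrt[(2/n) × (1 - rho²) × (1 + 1/(2n-4))]

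**Numbers for n = 120.** Both t quantiles are 1.970 and sqrt(2/120) = 0.1291, so the ANOVA half-width is 0.254 SD. The width ratio reduces to sqrt(1 - rho²) × sqrt(1 + 1/236) = sqrt(1 - rho²) × 1.0021.

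| rho | CI width, ANCOVA/ANOVA | Change | Equivalent sample-size factor |
|---|---|---|---|
| 0 | 1.002 | +0.2% | 0.996 |
| 0.1 | 0.997 | -0.3% | 1.006 |
| 0.2 | 0.982 | -2% | 1.037 |
| 0.3 | 0.956 | -4% | 1.094 |
| 0.5 | 0.868 | -13% | 1.328 |
| 0.6 | 0.802 | -20% | 1.556 |
| 0.7 | 0.716 | -28% | 1.952 |

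With n = 135 the ratios agree within 0.001.

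**As fold factors (SD 1.5, n = 120).** The unadjusted CI runs from the ratio divided by 1.303 to the ratio times 1.303, since 2^(0.254 × 1.5) = 1.303. With adjustment the factor is 1.288 at rho 0.3 and 1.258 at rho 0.5.

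**Chance imbalance.** The 95% limit for a difference in mean baseline is 1.96 × sqrt(2/120) = 0.253 SD. It moves the unadjusted ratio by 2^(rho × 0.253 × 1.5), a factor of 1.08 at rho 0.3 and 1.14 at rho 0.5.

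**Validity.** In simulation (3,000 data sets at each of rho 0, 0.3, 0.5 and 0.7, n = 120), coverage lay between 94.8% and 95.6% for both models. The mean width ratios were 1.002, 0.956, 0.867 and 0.715, in agreement with the formula.

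The calculation covers the baseline titer only. Any further gain from the age and risk strata is not quantified.

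**The case against.** The strongest case against is that nothing here is wrong. A two-group ANOVA after a randomised Day 1 assignment is a valid estimator with correct coverage. Sections 1.3 and 4.3.4 say no immunogenicity hypothesis is tested, and the SAP sets no margin or precision target for this ratio. Continuation to Subcohorts C and D depends on Subcohort B results (Table 1, footnote d), but not on a stated limit for the ratio. All of this stands, and it limits the weight of the point.

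The size of the gain is also assumed. Baseline and outcome lie one to four years and one or two active doses apart, so the correlation could be low. At 0.2 or less the gain is negligible. That stands too, but the cost of adjusting when the correlation is zero is 0.2% in width.

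Baseline is not ignored: fold increases are tabulated (Section 4.3.4.1.1), key assays are analysed by age and risk subgroup (Sections 2.4 and 4.3.4), and baseline factors are explored descriptively. These outputs can show an imbalance, but none of them adjusts the ratio.

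Selection through consent or PPI exclusions is a different problem from chance imbalance. Adjustment corrects it only as far as it acts through the covariates in the model.

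A reader might also infer from the word titers, followed by exponentiation, that the plan exponentiates a difference of raw titers. The document does not support that. Section 5.3 follows Section 4.3, where geometric means are built on log2 values, and exponentiating to a GMT ratio makes sense only for log titers. The omission of log2 is a wording slip.

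**Conclusion.** The point holds as one of efficiency and of protection against imbalance in measured baseline factors. The model omits a baseline titer that is planned in every subcohort and two factors used to stratify randomisation, and the only sensitivity analysis does not bring them in. It would be wrong to conclude that the planned intervals are invalid or that the ANOVA is biased by chance imbalance: under randomisation, coverage is nominal.

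With 120 per group, the change in CI width runs from +0.2% at rho 0 through -4% at 0.3 to -20% at 0.6. It rests on an assumed correlation and on a linear relation between log titers with equal variances. The change is worth making because the possible gain is much larger than the possible loss. It does not affect any test or decision rule in the SAP.

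**What to change.** In Section 5.3, for the humoral assays summarised by geometric means:

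- Fit an ANCOVA on log2 titer with group, log2 baseline titer of the same assay (taken before the first vaccination), and the age and risk strata.
- Report 2^(difference) with its 95% CI.
- State one LLOQ rule for the covariate, for example LLOQ/2. Section 4.3.3 uses LLOQ/2 for geometric means and LLOQ for fold increases, so the choice must be explicit.
- Do not use the titer taken just before revaccination as the covariate. Day 1 vaccination affects it in the active-first group, so adjusting for it would change what is estimated.
- Keep the unadjusted ANOVA and the Welch analysis as sensitivity analyses.
- As an editorial point only, write log2 titers as the dependent variable.

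The cost is SAP wording and one model line, with no new data. The small downside is that participants without a baseline sample drop out of the adjusted model. Their number should be reported, and the unadjusted analysis retains them.

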### 5.4. Efficacy Analysis

#### 5.4.1. Exploratory Efficacy Variable(s)

##### 5.4.1.1. Definition

Other exploratory efficacy endpoints are:

- **First occurrence of RT-PCR-confirmed RSV-mediated LRTD during the second RSV season and during the third RSV season according to Case Definition 1**

This is defined similarly as the primary endpoint, but only counted in the respective RSV season. The baseline assessment for the second RSV season is the Day 365 (Month 12) visit and for the third RSV season it is the Day 730 (Month 24) visit (see Section 2.1). New onset or worsening is defined similarly as for the primary endpoint, by comparing symptoms occurring during the ARI episode to symptoms reported at the new baseline (instead of by comparing to Day 1). First occurrence of a considered endpoint during the second or third RSV season is defined as the first episode of the considered endpoint in a given RSV season (regardless A or B strain, unless otherwise specified).

- **First occurrence of RT-PCR-confirmed RSV-mediated LRTD over season two and three and over all three RSV seasons according Case Definition 1**

This is defined similarly as the primary endpoint but taking into account events over season two and three and over all three seasons. The baseline assessment for the second RSV season is the Day 365 (Month 12) visit and for the third RSV season it is the Day 730 (Month 24) visit (see Section 2.1). New onset or worsening is defined similarly as for the primary endpoint, by comparing symptoms occurring during the ARI episode to symptoms reported at the new baseline (instead of comparing to Day 1). When evaluating the vaccine efficacy over season two and three or over all three seasons, first occurrence of a considered endpoint over two or three seasons is defined as the first episode over the two or three periods (regardless A or B strain, unless otherwise specified).

The following exploratory efficacy endpoints, are defined similarly as the corresponding endpoints during the first RSV season (see Section 4.4.3 and 4.4.4), but baseline, new onset or worsening and first occurrence are defined the same way as for RT-PCR-confirmed RSV-mediated LRTD, during the second and third RSV season and over season two and three or over all three RSV seasons. These endpoints might also be explored during the second or third RSV season and across season two and three or across all three RSV seasons.

- **First occurrence of any RT-PCR-confirmed RSV ARI**
- **First occurrence of any RT-PCR-confirmed RSV A ARI, based on the DDL assay**
- **First occurrence of any RT-PCR-confirmed RSV B ARI, based on the DDL assay**
- **First occurrence of RT-PCR-confirmed RSV-A-mediated LRTD according to Case Definition 1, based on the DDL assay**
- **First occurrence of RT-PCR-confirmed RSV-B-mediated LRTD according to Case Definition 1, based on the DDL assay**
- **First occurrence of potential complications (according to the Phase 3 definition; see Section 5.8) of respiratory disease linked to an RT-PCR confirmed RSV ARI**
- **First occurrence of hospitalization linked to an RT-PCR confirmed RSV ARI**
- **First occurrence of pneumonia linked to an RT-PCR confirmed RSV ARI**

Pneumonia is defined as:

- X-ray confirmed pneumonia (as assessed on the eCRF diagnostic tests form: diagnosis of pneumonia confirmed by chest X-ray) *OR*

- Radiological confirmed pneumonia (as assessed on the eCRF diagnostic tests form: diagnosis of pneumonia confirmed by chest X-ray, CT-scan or MRI)

#### 5.4.1.2. Analysis Methods

For all exploratory efficacy endpoints an exact Poisson model, as described in the primary efficacy analysis (see Section 4.4.2.2) will be performed, based on the respective PPE population.

For exploratory endpoints regarding only season one data, the follow-up time for cases is defined as the time between 14 days post-vaccination and the occurrence of the first event; for non-cases, it is the time between 14 days post-vaccination and the end of season visit. However, for participants that discontinued before the end of the season and had an event (according to the considered endpoint), the follow-up time is defined as the time between 14 days post-vaccination and the occurrence of the first event and for participants that discontinued before having an event, follow-up time is the time between 14 days post-vaccination and the date of last contact (date of discontinuation).

For exploratory endpoints regarding only season two data, the follow-up time for cases in season two is defined as the time between Day 365 visit and the occurrence of the first event (according to the considered endpoint) in the considered season, for non-cases in season two, it is the time between Day 365 visit and the Day 730 (Month 24) visit. However, for participants that discontinued before the end of the second season and had an event in season two (according to the considered endpoint), the follow-up time is defined as the time between Day 365 visit and the occurrence of the first event and for participants that discontinued before having an event in season two, follow-up time is the time between Day 365 visit and the date of last contact. Participants that discontinued prior to Day 365 visit as well as participants that are part of Revaccination Subcohort A will be excluded from the analysis.

For exploratory endpoints regarding only Season three data, the follow-up time for cases in Season three is defined as the time between the Day 730 (Month 24) visit and the occurrence of the first event (according to the considered endpoint) in the considered season, for non-cases in Season three, it is the time between the Day 730 visit and the end of the third season visit. However, for participants that discontinued before the end of the third season and had an event in Season three (according to the considered endpoint), the follow-up time is defined as the time between the Day 730 visit and the occurrence of the first event and for participants that discontinued before having an event in Season three, follow-up time is the time between the Day 730 visit and the date of last contact. Participants that discontinued prior to the Day 730 visit as well as participants that are part of Revaccination Subcohorts A and B will be excluded from the analysis.

In case Day 365 is missing the analysis, relative date will be used (day of vaccination + 364 days). In case Day 730 is missing the analysis, relative data will be used (day of vaccination + 729 days).

For exploratory endpoints over season two and three, the follow-up time is defined as the time between the Day 365 visit and the occurrence of the first event (according to the considered endpoint) in the two seasons, for non-cases, it is the time between the Day 365 visit and the end of the third season visit. However, for participants that discontinued before the end of the third season and had an event (according to the considered endpoint), the follow-up time is defined as the time between the Day 365 visit and the occurrence of the first event and for participants that discontinued before having an event, follow-up time is the time between the Day 365 visit and the date of last contact. Revaccination Subcohort A participants are not taken into account for these analyses. For Revaccination Subcohort B participants only the second season is taken into account: for cases during the second season, the follow-up time is the time between the Day 365 visit and the occurrence of the first event (according to the considered endpoint), for non-cases it is the time between the Day 365 visit and the Day 730 (Month 24) visit. Note that participants with an MPD expecting to impact the efficacy outcomes in season one or two are not taken into account for these analyses. For participants with an MPD expecting to impact the efficacy outcomes in season three, only the second season can be taken into account: for cases during the second season, the follow-up time is the time between the Day 365 visit and the occurrence of the first event (according to the considered endpoint), for non-cases it is the time between the Day 365 visit and the Day 730 (Month 24) visit.

For exploratory endpoints over three seasons (Season one, Season two and Season three), the follow-up time is defined as the time between 14 days post-vaccination (vaccination day + 14 days) and the occurrence of the first event (according to the considered endpoint) in the three seasons, for non-cases, it is the time between 14 days post-vaccination and the end of the third season visit. However, for participants that discontinued before the end of the third season and had an event (according to the considered endpoint), the follow-up time is defined as the time between 14 days post-vaccination and the occurrence of the first event and for participants that discontinued before having an event, follow-up time is the time between 14 days post-vaccination and the date of last contact. For Revaccination Subcohort A participants, only the first season is taken into account: for cases during the first season, the follow-up time is the time between 14 days post-vaccination and the occurrence of the first event (according to the considered endpoint), for non-cases it is the time between 14 days post-vaccination and end of first season visit. For Revaccination Subcohort B participants only the first two seasons are taken into account: for cases during the first two seasons, the follow-up time is the time between 14 days post-vaccination and the occurrence of the first event (according to the considered endpoint), for non-cases it is the time between 14 days post-vaccination and the Day 730 (Month 24) visit. Note that participants with an MPD expecting to impact the efficacy outcomes in season one are not taken into account for these analyses. For participants with an MPD expecting to impact the efficacy outcomes in season two, only the first season can be taken into account: for cases during the first season, the follow-up time is the time between 14 days post-vaccination and the occurrence of the first event (according to the considered endpoint), for non-cases it is the time between 14 days post-vaccination and the end of the first season visit. For participants with an MPD expecting to impact the efficacy outcomes in season three, only the first and second season can be taken into account: for cases during one of these two seasons, the follow-up time is the time between 14 days post-vaccination and the occurrence of the first event

(according to the considered endpoint), for non-cases it is the time between 14 days post-vaccination and the Day 730 (Month 24) visit.

The 95% exact 2-sided CI for the VE (1-relative risk rate) will be calculated from these regression models and graphically depicted with forest plots. In case of the model does not converge then it will be fitted with only the vaccination group as dependent variable.

Poisson models will be executed also for the subgroups defined in Section 2.4 only for the first occurrence of any RT-PCR-confirmed RSV ARI and for the first occurrence of RT-PCR-confirmed RSV-mediated LRTD according to Case Definition 1 for the second and third RSV season and across the three RSV seasons.

For the same endpoints, the following sensitivity analysis will also be performed, using the same model:

- based on the FAS (which also does not take into account the restriction on the onset [at least 14 days] and will count follow-up from vaccination on Day 1 onwards). RT-PCR results from samples that were out of stability, but tested RSV positive are taken into account in this analysis.
- based on the PPE set but excluding coinfections with other respiratory viruses based on GeneXpert and GenMark assay. This should be detected in one of the scheduled nasal or sputum samples linked to the respective ARI but should not necessarily be detected in the same sample as the one that resulted in RSV confirmation.
- based on the PPE set but only the participant reported symptoms (eDiary and eDevice) should be used to define case definitions.

For the sensitivity analysis focusing on data from the second RSV season only, participants from Revaccination Subcohort A and participants that discontinued earlier than the start of the second RSV season will be excluded. For the sensitivity analysis focusing on data from the third RSV season only, participants from Revaccination Subcohorts A and B and participants that discontinued earlier than the start of the third RSV season will be excluded. For sensitivity analysis focusing on data of RSV season two and three, participants from Revaccination Subcohorts A will be excluded and only data from the second RSV season for participants from Revaccination Subcohort B will be used. For sensitivity analysis focusing on data over three RSV seasons, only the first RSV season data will be used for participants from Revaccination Subcohort A and data from the first two RSV seasons for participants from Revaccination Subcohort B.

Kaplan Meier curves will be plotted for the time to first occurrence for any RT-PCR confirmed RSV ARI and for any RT-PCR confirmed RSV A and B ARI, across the three RSV seasons, based on the PPE set. The respective hazard ratios will also be calculated.

For participants with any RT-PCR-confirmed RSV disease during the second or third RSV season and across three RSV seasons, the median duration of the ARI episode will be summarized.

Complications linked to any RT-PCR confirmed RSV disease across the three RSV seasons will be summarized in a listing.

